9.6.3. SEVERE

An event requiring immediate intervention; causes significant discomfort.

9.7. ADVERSE EVENT REPORTING

Adverse event reporting requirements will be based on the time period in which the adverse event occurs. It is understood that many of the signs and symptoms observed with ICU patients are expected. However, these should still be reported as adverse events if they meet the definitions of the Protocol. A “clinical care” event should therefore be reported as an adverse event if it meets any of the definitions. A group of symptoms that can be combined under one diagnosis, should be reported as a single adverse event. If a group of symptoms cannot be combined under one diagnosis, the symptoms should be reported as separate adverse events. These events will be reported as the number of events per time of exposure to the device.

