Study Endpoints	
In this Pilot study four domains of interest have been designated. The four domains are:
 
 • Patient Safety: Safety Endpoint Measures include adverse events, laboratory safety parameters, vital signs, EKG, ventilation status and hemodynamic variables. • Clinical Efficacy: The Primary Clinical Efficacy Endpoint Measure is in-hospital; 28 and 60-day all-cause mortality. Time to renal recovery and necessity for chronic dialysis up to day 60 will also be determined. Additional efficacy endpoints include time to intensive care unit (ICU) discharge, and time to hospital discharge. • Device Integrity and Performance: The Endpoint Measure is SCD use without failure. This measure will help assess the integrity and performance of the SCD device. • SCD Mode of Action: Exploratory Endpoint Measures will include inflammatory cytokines, cell activation parameters and biomarkers at clinical sites with this capability. The analysis will be performed at a central laboratory.
Assessment of Device Integrity and Performance	
Criteria for assessment of device integrity and performance include:
 
 • Significant Clotting within the Device as assessed by visual inspection. • Evidence of leakage (i.e., cracking/breakage of a port, connector, hemofilter cartridge or tubing).

	
 Any unforeseen malfunction that results in the need for discontinuation.
Study Populations	Pediatric patients with a body weight (BW) between ≥ 10 and ≤ 20 kg receiving care in the Intensive Care Units of each participating hospital will be screened daily and identified for participation in the trial.
Study Design	This is an open-label, multi-center Pilot study.
Approximate Number of Subjects	Up to 10 patients will be enrolled in this study.
Approximate Number of Centers	Up to 7 Clinical Centers in the United States will participate in this study.
Duration of Subject Participation	Each patient will be followed for 60 days following enrollment.

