	
 4. Presence of preexisting advanced chronic renal failure (i.e., ESRD) requiring chronic renal replacement therapy prior to this episode of acute kidney injury or with pre-existing chronic kidney disease (CKD) defined as an eGFR<30 ml/min/1.73m². Patients who have never seen a pediatric nephrologist will be assumed not to have pre-existing CKD. 5. AKI occurring in the setting of burns, obstructive uropathy, scleroderma renal crisis, atheroembolism, functional or surgical nephrectomy, cyclosporine, or tacrolimus nephrotoxicity. 6. Metastatic malignancy which is actively being treated or may be treated by chemotherapy or radiation during the subsequent three month period after study therapy. 7. Chronic immunosuppression with the exception of corticosteroids up to a dose of 10 mg per day. 8. Known positive HIV or AIDS or COVID-19 9. Current Do Not Attempt Resuscitation (DNAR), Allow Natural Death (AND), or withdrawal of care status, or anticipated change in status within the next 7 days. 10. Patient not expected to survive 28 days because of an irreversible medical condition. (This is not restrictive to AKI, and may include situations such as the presence of irreversible brain damage, untreatable malignancy, inoperable life threatening condition, or any condition to which therapy is regarded as futile by the PI.) 11. Any medical condition that the Investigator thinks may interfere with the study objectives. 12. Treating clinician does not feel it is in the best interest of the patient 13. Platelet count <15,000/mm³ at time of screening. 14. Concurrent enrollment in another interventional clinical trial. Patients enrolled in clinical trials where only measurements and/or samples are taken (NO TEST DEVICE OR TEST DRUG USED) are allowed to participate. 15. Use of any other investigational drug or device within the previous 30 days. 16. Use of an AN-69 hemofilter membranes
Evaluation Plan	The primary evaluation of this study will be safety and all-cause mortality or dialysis dependency through 60 days post-enrollment. Additional endpoints will be time on CRRT, total ICU and hospital days. Mortality and dialysis dependency rates will be compared to historical controls.

LIST OF ABBREVIATIONS

ACD-A	Anticoagulant Citrate Dextrose- Formula A
AE	Adverse Event
AKI	Acute Kidney Injury
AIDS	Acquired Immunodeficiency Syndrome
AND	Allow Natural Death
ARDS	Acute Respiratory Distress Syndrome
ARF	Acute Renal Failure

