2.4.2 SAFETY RESULTS

A summary of all adverse events (AEs) observed in the 35 subjects is presented in **Table 3**. The AEs observed were those expected for a critically ill patient population with acute renal failure and/or in an ICU setting.

Table 3. Summary of Adverse Events ARF-002

Adverse Events	Number of Subjects with Events N (% of 35)	Number of Events % of 199 (n/199)
Total adverse events	33 (94%)	199
Serious adverse event	23 (66%)	14.1% (28/199)
Unanticipated Adverse Device	0 (0%)	0.0% (0/199)
Relationship to Study*		
Unrelated to study therapy	32 (91%)	93.5% (186/199)
Possibly related to study therapy	8 (23%)	6.0% (12/199)
Probably related to study therapy	0 (0%)	0.0% (0/199)
Definitely related to study	1 (3%)	0.5% (1/199)
Outcome		
Resolved w/ sequelae	14 (40%)	13.6% (27/199)
Resolved w/out sequelae	25 (71%)	64.3% (128/199)
Continuing	11 (31%)	11.1% (22/199)
Death	11 (31%)	5.5% (11/199)
Reported as Unknown	3 (9%)	5.5% (11/199)
Frequency		
Single Episode	29 (83%)	54.3% (108/199)
Intermittent	16 (46%)	21.1% (42/199)
Continuous	16 (46%)	24.1% (48/199)
Reported as Unknown	1 (3%)	0.5% (1/199)

Adverse Events	Number of Subjects with Events N (% of 35)	Number of Events % of 199 (n/199)
Severity		
Mild	21 (60%)	34.7% (69/199)
Moderate	25 (71%)	51.8% (103/199)
Severe	19 (54%)	13.6% (27/199)

*Subjects experienced more than one AE, therefore, numbers do not add up to N=22 (number of subjects experiencing any adverse event).

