6.5 SCD TREATMENT PERIOD

The SCD Treatment Period begins when the subject starts treatment and will continue up to a maximum of 240 hours from the time of Treatment Start. A subject may begin CRRT therapy and SCD treatment at the same time, which would also mark the beginning of the SCD Treatment Period.

This treatment period has been broken into ten 24 hour time periods. It ends when the subject has reached 240 hours in the treatment period or when the subject meets the termination criteria outlined in **Section 7.2** as determined by the Principal Investigator or Medical Team at the participating Clinical Site.

All tests are scheduled on a 24 hour cycle, or once a day, and can be scheduled to be drawn around each participating site's ICU blood drawing schedule, with the exception of any test that requires a specific draw frequency.

The following information will be obtained for subjects enrolled during the SCD treatment period on a daily basis unless otherwise specified:

- **Vital Signs/Physical Assessment**
 - Temperature
 - Blood Pressure, heart rate
 - Urine Output (previous 24 hours)
 - Net Fluid Balance (previous 24 hours)
- **Clinical Laboratory Tests**
 - CBC with differential
 - BUN, Creatinine
 - Na, K, Cl, HCO₃, Ca, ionized Ca, Mg, PO₄
 - ALT, AST, Bilirubin, ALP, Total Protein, Albumin, Glucose
- **Respiratory**
 - Status – Ventilator support (yes/no; date of intubation or extubation, as applicable)
 - If on Vent: FiO₂
 - If on Vent with an arterial line: Arterial Blood Gas

- If on Vent without an arterial line: Arterial Blood Gas (if completed as standard of care)
- ECMO Status (yes/no; date of cannulation or decannulation as applicable)
- **Blood for Research**
 - Collect at hours 48, 96, 144, 192 and end of SCD treatment (\pm 6 hours). Blood for biomarkers will be collected as close as possible to the time of SCD scheduled changes in the days required (\pm 6 hours) if practical and within window.
 - Blood sample will be sent to an outside laboratory (Innovative Therapies) for testing of biomarkers
- **CRRT Parameters (Start at hour 0)**
 - Parameters include modality, blood flow rate, net fluid removal, dialysate or replacement solution flow rate, citrate infusion rate, calcium replacement rate.
 - System performance (circuit survival - event driven)
 - Post filter ionized calcium

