Besides the test of the hypothesis the study is focused on observable, empirical and laboratory determinations of subject safety while on the SCD. Previous human trials have been conducted on the SCD device and the protocol contains a review of AE and SAE data from all SCD human studies and findings from those studies contributed to constructing the investigative safety profile. Safety endpoint measures specified in the protocol include adverse events, laboratory safety parameters, vital signs, ventilation status and hemodynamic variables. Device integrity and performance measurements are also defined as are circumstances which demand premature termination of SCD treatment.

Prolonged exposure to the SCD is anticipated to result in superior outcomes, although as noted above, this pilot study is not designed to assess for efficacy. However, we understand that a minimum amount of exposure to the SCD will be required for an appropriate safety analysis and for making any inference regarding efficacy. The ppCRRT experience demonstrated that the majority of patients (201/370) received CRRT for 1 to 7 days and exhibited 65% survival (Symons et al CJASN 2007 Table7).

This trial is an early safety efficacy study but is not powered for statistical significance. Insights into a comparison of historical controls matched to SCD treated subjects will utilize the ppCRRT Registry to match for: etiology of AKI, co-morbidities, CRRT modality, dose and form of anticoagulant, adverse events. [10]

The ppCRRT Registry has data fields for the primary reason for CRRT, including AKI and its cause, as well as co-morbidities which will be matched for primary organ system involvement. The CRRT modality was evenly distributed between convective and diffusive modality, with 60% of the convective modalities provided as CVVH and 40% as CVVHDF. The anticoagulant protocol will be standardized with ACD-A/CaCl₂ and all centers used the same protocol in ppCRRT Registry as outlined in this study protocol. Thus, the ppCRRT Registry dataset will be able to be matched to our study subject cohort. Also as noted above, subjects will be matched for age, size and PRISM II score.

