The Prospective Pediatric CRRT (ppCRRT) database will be used as a control for the CRRT treatment related factors including: patient age, gender, primary cause of AKI, total treatment duration, CRRT modality (CVVH, CVVHD, CVVHDF), CRRT small solute clearance (ml/1.73m²/hour), baseline estimated GFR (using the original Schwartz formula, which was used in the ppCRRT), urine output in the 24 hours prior to CRRT initiation (ml/kg/hour), percent fluid overload at CRRT initiation based on admission ICU weight, vasoactive medication number at time of CRRT initiation and mean airway pressure at CRRT initiation.

An additional analysis will also evaluate patients who have achieved targeted iCa levels during 90% of treatment time and those who do not.

In summary this protocol meets all criteria necessary for clinical scientific inquiry related to a test of hypothesis in a well monitored environment focused on subject safety during the conduct of the study. Basic statistics will be performed on the data sets along with historical data comparisons and subjected to subset analysis where appropriate. The results will help to guide the design of a future pivotal study of this device.

The rational for therapy, study objectives and endpoints, design, inclusion and exclusion criteria are explicitly defined. Subject safety parameters are well documented including safety reporting, safety observations and assays, procedures for subject withdrawal and study discontinuation criteria along with monitoring device integrity and performance. Lastly, a review of all prior SCD human study safety data is included in the protocol for full disclosure to study investigators and the informed consent document includes a full description of all known and potential risks of the device treatment.

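### Section 9.7 names one adverse event summary, a pooled rate per device time, which does not show how many of the up to 10 children were affected

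*Combined protocol and SAP*

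**What the plan says.** The closing sentence of the opening paragraph of section 9.7 fixes the summary: "These events will be reported as the number of events per time of exposure to the device". The same paragraph sets the counting rule: "If a group of symptoms cannot be combined under one diagnosis, the symptoms should be reported as separate adverse events". One very sick child can therefore add many events to the numerator.

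The synopsis states "Up to 10 patients will be enrolled in this study". Section 6.5 says that treatment "will continue up to a maximum of 240 hours from the time of Treatment Start", so the largest possible denominator is 10 children × 10 days = 100 device-days.

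No other adverse event summary is specified. Section 12 says "Basic statistics will be performed on the data sets along with historical data comparisons", and also "This trial is an early safety efficacy study but is not powered for statistical significance". Section 11 has the DSMB look at adverse event incidence without defining its unit.

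For earlier studies of the device, Table 3 (section 2.4.2) and Table 4 (section 2.5.2) give subjects with events and event counts side by side.

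**The concern.** Safety is the primary objective, and adverse events come first among the safety measures in section 3.2. The DSMB, the ethics boards and the designers of the later pivotal study will want to know what share of treated children had an event, a serious event or a related event. A rate pooled over device time answers a different question. It counts repeat events in one child in the same way as first events in several children, and the children treated longest supply most of the denominator.

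The earlier studies are the natural reference, and their tables include a per-subject column. If this pilot reports only what section 9.7 names, that comparison cannot be made from the reported summary.

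The point concerns the unit of analysis. Which events belong in the numerator is a separate matter.

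**Working it through.** The plan prints no power, error rate, adverse event rate or interval, so there is no design figure to reproduce. The printed percentages from earlier studies were checked instead: 33/35 = 94%, 28/199 = 14.1% and 45/69 = 65.2%. All three agree.

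**Inputs**
- Up to 10 children, at most 240 hours each (synopsis; section 6.5).
- ARF-002: 199 events, 33 of 35 subjects with any event; 28 serious events in 23 of 35 (Table 3).
- SCD-003, device arm: 80 serious events in 45 of 69 subjects (Table 4).
- Assumptions: all 10 children enrolled, each treated for 10 days. The documents do not give the between-child dispersion.

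**Step 1. What the rate cannot separate (no distribution assumed)**

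| Pattern | Events / device-days | Rate per 100 | Children affected | Exact 95% interval |
|---|---|---|---|---|
| One event in each of ten children | 10/100 | 10 | 10/10 | 69.2% to 100% |
| Ten events in one child | 10/100 | 10 | 1/10 | 0.3% to 44.5% |

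The lower limit for 10/10 is 0.025^(1/10) = 0.692.

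**Step 2. Influence of one child**

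The ARF-002 mean is 199/35 = 5.69 events per subject. Ten children at that mean have about 57 events, or 57 per 100 device-days.
- If one child has 15 of the 57 (26%), the other nine give 42/90 = 46.7 per 100.
- If one child has 25 of the 57 (44%), the other nine give 32/90 = 35.6 per 100.

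In simulation with 10 children and equal exposure, the most affected child supplies a median 17% of events with no overdispersion, and 24% (95th percentile 36%) at a variance/mean ratio of 3.5. The first case is therefore near typical at that ratio, and the second is extreme.

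**Step 3. Comparison with earlier studies**

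Table 3 can be read as 94% of subjects with any event and 66% with a serious one. Table 4 gives 65.2% of the device arm with a serious event. A figure per device-day matches none of these, and neither table prints device time that would convert its event counts.

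**Step 4. If someone puts a Poisson interval on the rate**

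- All events, ARF-002: Poisson expects 35 × exp(−5.69) = 0.12 event-free subjects. There were 2 (P of 2 or more = 0.006).
- A negative binomial with that mean solves (1 + 5.69/k)^(−k) = 2/35 at k = 2.3. The variance/mean ratio is 1 + 5.69/2.3 = 3.5.
- At that dispersion, with 10 children and equal exposure, a nominal 95% Poisson interval covers about 72% (83% at k = 5, 56% at k = 1).
- Serious events, ARF-002: the mean is 28/35 = 0.80, and 35 × exp(−0.80) = 15.7 event-free expected against 12 seen.
- Serious events, SCD-003 device arm: the mean is 80/69 = 1.16, and 69 × exp(−1.16) = 21.6 expected against 24 seen. The fitted variance/mean ratio is about 1.2, and Poisson coverage near that value is about 96%.

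Any shortfall in coverage is thus a possibility for all adverse events, and is not seen for serious events.

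**Step 5. What the proposed summary would give**

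Exact 95% intervals at n = 10: 0/10 gives 0 to 30.8%; 1/10 gives 0.3% to 44.5%; 2/10 gives 2.5% to 55.6%; 3/10 gives 6.7% to 65.2%. For the event rate, a t interval on between-child variation is about 2.0 times as wide as the Poisson interval at a variance/mean ratio of 3.5 and covers about 93%. At a ratio of 5 it is 2.4 times as wide and covers about 91%.

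**The case against.** The strongest reply is that section 9.7 does not exclude a per-child table. Its sentence closes a paragraph on event coding, the DSMB will set its own displays, and the sponsor tabulated both units before. The data are recorded per child, so the table could be made later. This is fair as far as it goes: that adverse events will be reported in no other way is an inference from silence. But the plan names one summary, and its main safety table should not be left to be chosen after the data are seen.

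A rate also has a real merit. It allows for unequal treatment time, which a simple proportion does not. That is a reason to keep it beside the proportion.

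A reader might further infer that any usual interval around the rate would be too narrow. The documents do not support this, for four reasons.
- No adverse event interval is planned.
- Unequal exposure alone could explain the two event-free subjects in ARF-002. Suppose a constant Poisson rate and, as an assumption, treatment for 1 to 7 whole days, each equally likely. The rate is then 5.69/4 = 1.42 per day, and 35 × the average of exp(−1.42t) gives 1.6 event-free subjects. For 1 to 10 days it gives 1.9. A rate per device time would adjust for this.
- The value k = 2.3 rests on two event-free subjects in an adult study (mean age 56.3). The exact interval for 2/35 (0.7% to 19.2%) allows k from about 18.6 down to 0.8. The footnote to Table 3 also gives 22 subjects with any event where the table gives 33.
- The serious event counts show little or no overdispersion.

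This objection stands in full against a general claim about intervals. It leaves the unit-of-analysis point untouched.

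**Conclusion.** The point holds as one about the unit of analysis. At n = 10 the specified rate does not give the share of children affected: the same 10 events per 100 device-days fits 1 child in 10 or 10 in 10. That conclusion needs no dispersion value, and the figure of 100 device-days is only a convenient assumption.

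A reader might also infer that one child can dominate the primary safety result. That is too strong. Section 3.2 lists adverse events among several safety measures. Section 3.1 words the primary objective around mortality and dialysis dependency, and the synopsis says "The primary evaluation of this study will be safety and all-cause mortality or dialysis dependency through 60 days post-enrollment". Death and dialysis dependency count at most once per child. What one child can pull is the adverse event part of the safety evaluation.

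The 72% coverage figure is conditional on k = 2.3, equal exposure and a Poisson interval that nobody has planned. It supports a precaution about how an interval should be built if one is added, and nothing more. The trial is a single-arm pilot with no adverse event hypothesis or threshold, so the consequence is for the clarity and comparability of the safety report.

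**What to change.** In section 9.7:
- Add, as the main adverse event table, the number and percentage of children with at least one event: all, serious, related, and by category. Give exact (Clopper-Pearson) 95% intervals.
- Keep events per device time as a secondary summary.
- State that any interval on that rate will be based on between-child variation (negative binomial, robust or child-level bootstrap), with the caution that such methods are themselves approximate with 10 children.

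This takes one or two sentences and one more table, with no new data collection. The drawback is that the per-child intervals will be wide: even 0/10 leaves an upper limit of 30.8%. That width is a fair statement of what 10 children can show.

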9.7.1. SCREENING AND ENROLLMENT PERIOD

Only adverse events, serious and not serious, directly related to the screening procedures will be captured during this period. Unrelated clinical adverse events that occur prior to SCD treatment will be considered part of the medical history.

9.7.2. TREATMENT PERIOD THROUGH END OF STUDY

All adverse events that occur from the time of SCD start will be recorded as follows:

- Serious Adverse Events (identified in **Section 9.2**) will be recorded until Day 60 after enrollment, death, or subject withdrawal of study consent, whichever occurs first.
- Non-serious adverse events will be recorded until end of 120 hours after the SCD Treatment Period ends, death, subject withdrawal of study consent or until ICU discharge, whichever occurs first.

Any serious adverse event (regardless of relationship to the

treatment) occurring from the time of enrollment through end of study must be reported to the CCC and DCC at Cincinnati Children's Hospital, within 24 hours of knowledge of the event.

Each clinical trial site will be supplied with written SAE reporting instructions, SAE reporting forms and contact information for reporting of serious adverse events.

For any AE that is ongoing at the time of the initial report, periodic follow-up information will be required until the adverse event is resolved or the patient is no longer in the study, whichever occurs first.

The Investigator is responsible for all adverse events reporting to the Institutional Review Board (IRB) according to the requirements of the IRB and for providing clinical trial monitors with all medical records needed to source-verify the adverse events.

